3.8.3 Definition of core phase data

After completing the core phase, subjects have the option to enter the extension study. All core phase data are entered in the database for core phase. All extension data will be entered in the database for extension phase.

For subjects who do not enter the extension study, all collected data will be considered as core phase data.

For subjects who enter the extension study, any measurement or event prior to the first dose of the extension study drug that is recorded on the core phase eCRF in the core phase database. For running records (e.g., adverse events), any event starting prior to the first extension study drug that is recorded on core phase eCRF in the core phase database.

3.8.4 Nominal visits and visit windows

As a general rule for by-visit summaries, nominal visits should be used to present efficacy data (including QoL and PRO assessments) and visit windows to present safety data.

3.8.4.1 Nominal visits

Nominal visits (i.e., the visits as collected in the database) will be used for by-visit summaries of EDSS, MRI, [REDACTED] and ophthalmic exam (OCT). Data from unscheduled visits will not be summarized in by-visit summaries, unless otherwise specified.

For subjects who complete the study drug before the nominal 24 month visit, the EOT visit (Visit 777) will be remapped to the next scheduled visit.

For subjects who discontinue the study drug prematurely, the EOT visit (Visit 777) and the follow-up visit (Visit 501) are not timepoint specific visits and will be remapped based on the following rules:

- If these visits fall into a specific visit window and the corresponding scheduled visit is missing, then these visits will be remapped to be that scheduled visit. The visit windows are defined as within 5 days of the monthly scheduled visit (i.e., Visits 4, 5, 6 and 7), or within 10 days of the quarterly scheduled visit (i.e., Visits 8, 9, 10, 11, 12, 13 and 14).
- If these visits fall into a specific visit window and the corresponding scheduled visit (e.g., Visit X) is not missing, then these visits will be assigned a visit number with a decimal place where the visit number depends on whether the corresponding scheduled visit occurs before (e.g., Visit X.1 or Visit X.2 if Visit X.1 already exists etc.) or after these visits (e.g., Visit X-1.1 or Visit X-1.2 if Visit X-1.1 already exists etc.)
- If these visits do not fall into a specific visit window but fall in between 2 consecutive scheduled visit windows (e.g., between visit windows of Visit X and Visit X+1), then these visits will be assigned a visit number with a decimal place (e.g., Visit X.1 or Visit X.2 if Visit X.1 already exists etc.).

The remapped visits (e.g., Visit X) will be treated as nominal visits in the by-visit summaries.

For subjects who discontinue study drug prematurely and have the abbreviated visits, all the abbreviated visits (if different visit numbering is used) will be mapped to the corresponding regular visits and will be treated as nominal visits in the by-visit summaries.

3.8.4.2 Visits windows

For data not listed in [Section 3.8.4.1](#), visit-windows will be defined and used for the by-visit summaries. Visit-windows will only be defined for post-baseline visits and applied to post-baseline data (including both scheduled and unscheduled visit). Based on the study assessment schedule as specified in the study protocol, visit-windows are defined by a set of days around each nominal visit target day.

Visit-windows for vital signs, laboratory assessments, ophthalmologic examination (excluding OCT), pulmonary function tests, and ECG are provided in Table 3-4 to Table 3-9. These visit-windows will not be applied to any data related to the first dose or second dose or restart dose monitoring which will be summarized separately.

When visit-windows are used, all post-baseline visits will be re-aligned, i.e., they will be mapped into one of the visit-windows. E.g., if a subject's *Month 1* visit is delayed and occurs on Day 47, then it will be re-aligned to visit-window *Month 2*. As a result, it is possible that several assessments may fall into one particular visit-window. Statistical approaches to handle multiple visits in a given visit-window are described in [Section 3.8.6](#). Tables displaying summary statistics "by visit" will also use the term visit-window as column header; this is to remind the reviewer that multiple assessments of a subject might be summarized.

Table 3-4 Visit-windows for vital signs, physical development, and laboratory values (hematology/blood chemistry other than liver panel)

Visit	Start day	Target Day	End day
Week 2	1	14	22
Month 1	23	30	45
Month 2	46	60	75
Month 3	76	90	135
Month 6	136	180	225
Month 9	226	270	315
Month 12	316	360	405
Month 15	406	450	495
Month 18	496	540	585
Month 21	586	630	675
Month 24	676	720	765

Table 3-5 Visit-windows for urinalysis

Visit	Start day	Target Day	End day
Month 6	1	180	270
Month 12	271	360	540
Month 24	541	720	765

Table 3-6 Visit-windows for liver panel

Visit	Start day	Target Day	End day
Week 2	1	14	22
Month 1	23	30	37
Month 1.5	38	45	52
Month 2	53	60	75
Month 3	76	90	105
Month 4	106	120	135
Month 5	136	150	165
Month 6	166	180	225
Month 9	226	270	315
Month 12	316	360	405
Month 15	406	450	495
Month 18	496	540	585
Month 21	586	630	675
Month 24	676	720	765

Table 3-7 Visit-windows for ophthalmologic examination (excluding OCT)

Visit	Start day	Target Day	End day
Month 3	1	90	135
Month 6	136	180	225
Month 9*	226	270	315
Month 12*	316	360	450
Month 18*	451	540	630
Month 24	631	720	765

*Only for a subset of subjects.

Table 3-8 Visit-windows for pulmonary function tests

Visit	Start day	Target Day	End day
Month 1	1	30	60
Month 3	61	90	135
Month 6	136	180	270
Month 12	271	360	450
Month 18	451	540	630
Month 24	631	720	765

Table 3-9 Visit-windows for ECG

Visit	Start day	Target Day	End day
Month 1	1	30	195
Month 12	196	360	540
Month 24	541	720	765

3.8.4.3 Time points for first dose monitoring ECG and Vital signs

For the first dose monitoring ECG, data will be summarized for the following time points:

- Day 1 pre-dose
- Day 1 post-dose (6 hours)
- Day 1 post-dose (>6 hours) (derived as the mean of all day 1 ECG values after 6 hours per time label (including unscheduled values).

Unscheduled ECG measured between the day 1 pre-dose and the 6 hours post-dose will not be summarized but reported in the data listing only. For the second dose monitoring ECG, data will be summarized similarly.

For the first dose monitoring vital signs, data will be summarized for the following time points:

- Day 1 pre-dose
- 1 hour post-dose
- 2 hours post-dose
- 3 hours post-dose
- 4 hours post-dose

- 5 hours post-dose
- 6 hours post-dose

The vital sign values at specified hours as recorded in the database will be used. For the second dose/dose increase/restart first and second dose monitoring vital signs, data will be summarized similarly.

Additional vital sign for extended monitoring after the 6 hour time-point will not be summarized but reported in the data listing only.

3.8.5 Safety data cutoff and visit windows for summaries on follow-up set

For safety summaries on the safety set, only core phase data (defined in 3.8.3) which are within 45 days (5 times the half-life of FTY720, 9 days) after the last dose of study drug. For safety summaries on the follow-up set, all core phase data, including assessments or events more than 45 days after the last dose of study drug in core phase, will be considered.

The time-windows below will be used in summaries on the follow-up set.

- 1) Day 1 to 45 after drug discontinuation
- 2) >Day 45 after drug discontinuation

For each of the time-window, assessments collected or events started during the specified day intervals after the last dose date will be used. The last dose date defined in Section 3.8.7 will be used to determine day windows.

3.8.6 Multiple assessments within visit windows

For visit windows defined in [Sections 3.8.4.2](#) and [3.8.5](#), multiple records may exist in one particular visit window. All results (scheduled and unscheduled) will be displayed in listings, but only one value (observed or derived) “representing” the subject will be selected for summary statistics by visit-window. The following rules (unless otherwise specified) will be applied to obtain one value per subject per visit-window which will be used in the by-visit summaries.

- For quantitative variables (i.e., continuous variables for which summary statistics and change from baseline tables will be provided), the average of the multiple records will be used.
- For qualitative variables (i.e., binary or nominal variables for which incidence rates and frequency distribution tables will be provided), the worst record (from scheduled and unscheduled visits) will be used. It is noted that in the analyses performed, worst case is always well defined.

Note that “Last assessment on study drug” is not like other visit-windows where multiple assessments could occur. The assessment to be summarized at that time point is the last on drug observation which is the last observation a subject has while he or she is on study drug. Therefore, the above multiple assessment rules do not apply.

In addition, the multiple assessment rules do not apply to the first dose/second dose/dose increase/restart dose monitoring data.

3.8.7 Last dose day of randomized study medication

The last dose date of the randomized study drug will be collected on three eCRFs:

- 1) The last date patient took study drug on the study phase completion eCRF,
- 2) The study drug discontinuation date on the study drug discontinuation eCRF, and
- 3) The last end date on the study drug administration record eCRF.

The last dose date recorded in the study phase completion eCRF (included in the CMP data panel with visit number 778) will be used.

4 Efficacy evaluation

Unless otherwise specified, all efficacy analyses will be based on the Full Analysis Set, following the intention-to-treat principle. Analysis of the primary efficacy variable will also be conducted on the per-protocol set, as well as the analyses on the key secondary variable. Treatment group estimates will be determined using least-squares means estimates.

All statistical models will be adjusted by the two randomization stratification factors: region and pubertal status reported in IVRS based on investigator's assessment. Pooling of regions with small patient count will be performed for better model fitting based on patient count in the region and geographic proximity. As a result, there will be three regions: East Europe, West Europe, rest of the regions (pooled by three small regions with <20 patients for each: Australia, Middle and South America, and North America). A stratification factor may also be considered to be removed from the model in presence of extremely small stratum with scarce information or given model converge problem.

4.1 Primary and key secondary variables

4.1.1 Primary variable

The primary efficacy variable is the annualized relapse rate (ARR), which is defined as the average number of confirmed relapses per year (i.e., the total number of confirmed relapses divided by the total number of days in the core phase multiplied by 365.25). The total number of days in the core phase is defined in section 4.1.2; the number of relapses will include all the confirmed relapses experienced during the corresponding observation period. The ARR can be calculated in two ways:

1. ARR (time-based)

The ARR (time-based) is calculated as the sum of the number of confirmed relapses of all subjects in the group divided by the sum of the number of days on study of all subjects in the group and multiplied by 365.25. The time-based ARR is the primary efficacy variable.

2. ARR (subject-based)

The ARR (subject-based) is calculated as the number of confirmed relapses divided by the number of days on study and multiplied by 365.25. The ARR of a treatment group is the mean of ARR of all subjects in the group.

4.1.2 Time in study for primary analysis

Time in study (days) (i.e., the number of days on study) for each subject will be calculated as the final study phase visit date– 1st core dose date +1.

Final study phase visit date is recorded on the study phase completion eCRF.

4.1.3 Key secondary efficacy variable

The key secondary variable is the annualized rate of new/newly enlarged T2 lesions (n/neT2).

4.2 Statistical methodology

The primary analysis pertaining to the primary efficacy objective will be based on the FAS, following the intention-to-treat principle.

4.2.1 Primary analysis

The null hypothesis for the primary analysis states that: there is no reduction in the annualized relapse rate (ARR) in the subjects treated with fingolimod compared to the ARR in subjects treated with IFN β -1a, while the alternative hypothesis states there is a reduction in the ARR in fingolimod treated subjects.

The test of the null hypothesis will be based on a negative binomial regression model with log link, using treatment, pubertal status (the stratification factor in IVRS), and region as factors and number of relapses within the previous two year before randomization as covariate. The primary analysis will be conducted on the FAS.

The response variable for this analysis is the number of confirmed relapses for each subject, and the quadratic variance estimate will be used. The natural log of (time in study in years for each subject) will be used as the offset to account for the varying lengths of subjects' time in the study. The null hypothesis will be rejected if the observed p-value is less than the significance level of 0.05.

Model-based estimates of the ARR (Least-squares mean, LSMean) and its 95% confidence intervals, ARR ratio and its 95% confidence intervals and p-value comparing fingolimod vs. IFN β -1a will be provided. The LSmean will be estimated with the OBSMARGINS option (abbreviated OM). The OM option allows the LSMEANS estimation to use the observed marginal distribution of the categorical covariates (region, pubertal status) rather than assuming equal weighting among the levels for each categorical covariate. Specification of the OM option will not affect the between-group comparison, i.e., p-value.

To control for the overall type-I error rate, a multiplicity adjustment as specified in [Section 4.2.2.1](#) will be applied to the primary and key secondary endpoints hypothesis testing. The 95% confidence intervals will not have any further adjustment for multiplicity.

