Section 6.7.2 was modified to include a single PK assessment in the Extension Phase to monitor blood concentrations after one month in the Extension Phase to allow for possible dose increase based on the blood concentrations of fingolimod for newly treated patients.

Section 9.1 was updated to update the Core Phase statistical analysis sets and to add the statistical analysis sets for the Extension Phase.

Section 9.5.1, 9.5.2, 9.5.3, 9.5.4 and 9.5.5 were updated to include the natural log as an offset for T2 lesion analysis, to add the Extension Phase efficacy and safety variables and to provide a PK assessment at Month 25.

Section 9.6 was updated to indicate there was no sample size calculation for the Extension Phase. The Extension Phase sample size is dependent on the number of patients that complete the Core Phase and enroll into the Extension Phase.

Appendix 2 was updated to indicate that First dose monitoring is required by the independent first dose monitoring team in the Extension Phase only for the first dose of medication in the Extension Phase.

Appendix 3 Section 15.5 Guidance on monitoring of patients with infections was updated to provide additional guidance regarding infections.

Additional minor clarifications and editorial changes were made throughout the protocol for clarity and consistency across sections.

Summary of previous amendments

Amendment 4: released 23-Oct 2014

Amendment rationale

Amendment 4 implemented modifications based on feedback from 1) the study advisory group, 2) infectious disease experts 3) Investigators enrolling patients in the clinical trial and 4) health authority input.

Inflammatory disease activity in MS is expressed as clinical relapses and as inflammatory lesions on MRI, both of which have been shown to be predictive of future MS relapse activity. The current protocol inclusion criterion defines a population with active disease based on prior relapses. This inclusion criterion is now being expanded to additionally allow patients with evidence of active disease based on recent MRI activity alone (presence of Gd-enhancing lesions within 6 months prior to randomization) to be enrolled. This change reflects the current clinical practice in pediatric MS where decision making for switching treatments is commonly based on MRI activity and will appropriately increase the pool of patients that can be considered for the study ([Banwell et al 2011](#), [Yeh et al 2011](#)).

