4.1 Inclusion criteria

Core Phase:

Patients eligible for inclusion in this study have to fulfill all of the following criteria:

1. Written informed consent must be obtained before any assessment is performed.

2. Male and female patients aged 10-17 years old*, inclusive (i.e., have not yet had their 18th birthday) at randomization.
3. A diagnosis of MS as defined by the revised consensus definition for pediatric MS, ([Krupp et al 2013](#), [Polman et al 2011](#)).
4. Central review of the diagnosis of pediatric MS will be required for all patients prior to randomization.
5. At least one MS relapse/attack during the previous year or two MS relapses in the previous two years prior to screening or evidence of one or more Gd enhancing lesions on MRI within 6 months prior to randomization (including screening MRI).
6. Expanded Disability Status Scale (EDSS) score of 0 to 5.5, inclusive.

*Exception: If, in a specific country, use of interferon- β -1a IM in children below a certain age is included in the Contraindications section of Avonex (interferon- β -1a IM) local product information, inclusion of such patients is not permitted in that country. E.g. the Russian Avonex product information lists use in children below the age of 12 years as a contraindication.

Fingolimod Extension Phase:

Criterion applies to all patients entering the Extension Phase.

1. Patients that originally met Core Phase Inclusion criteria and completed the Core phase on or off of study drug.

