9.4.2 Statistical model, hypothesis, and method of analysis

The null hypothesis for the primary analysis states that: there is no reduction in the annualized relapse rate (ARR) in the patients treated with fingolimod compared to the ARR in patients treated with IFN β -1a, while the alternative hypothesis states there is a reduction in the ARR in fingolimod treated patients.

The test of the hypotheses will be based on a negative binomial regression model with log link, using treatment, number of relapses in the previous two years prior to screening, pubertal status, and region as covariates. Study centers are consolidated by country. In order to minimize the impact of low-enrolling countries on the analysis (such as non-convergence of the analysis model), countries will be pooled into regions based on geographical proximity. Details will be provided in the statistical analysis plan prior to database lock.

The response variable for this analysis is the number of confirmed relapses for each patient, and the quadratic variance estimate will be used. The natural log of (time in study for each patient) will be used as the offset to account for the varying lengths of patients' time in the study. The null hypothesis will be rejected if the observed p-value is less than the significance level of 0.05.

Model-based estimates of the ARR (aggregated over each treatment group) and its 95% confidence intervals, ARR ratio and its 95% confidence intervals and p-value comparing fingolimod vs. IFN β -1a will be provided.

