4.2.2.4 MRI

MRI will be assessed at screening, Months 6, 12, 18, and 24 (end of study or early discontinuation) visits. Parameters collected at screening include: number and volume of T2 lesions, volume of T1 hypointense lesions, number and volume of Gd-enhancing lesions, and normalized brain volume. The following parameters will be collected at each post baseline visit:

- Number of new/newly enlarging T2 lesions (on each scheduled scan compared to previous scheduled scan and compared to the Screening scan)
- [REDACTED]
- Number of Gd-enhancing lesions (on each scheduled scan; optional for M18 scan)
- Volume of Gd-enhancing lesions (on each scheduled scan; optional for M18 scan)
- [REDACTED]
- [REDACTED]
- [REDACTED]
- [REDACTED]
- [REDACTED]

The number and volume of Gd-enhancing lesion data obtained less than 30 days after use of steroid for treatment of relapses will be excluded from the analysis.

The following is the complete list of the MRI endpoints, including the annualized rate of the number of new/newly enlarged T2 lesions (the designated key secondary endpoint) and the secondary endpoint of the number of T1 Gd-enhancing lesions per scan up to Month 24 (i.e., month 0 to EOS), which is also discussed in detail in [Section 4.2.2.2](#), as well as the exploratory endpoints. The time point of EOS is the last MRI scan in the core study. :

[figure not shown]
[figure not shown]
T2 lesions:

- Annualized rate of the number of new/newly enlarged T2 lesions up to Month 24 (i.e., Month 0 to EOS) and by visit (i.e., Month 0 to 6, Month 0 to 12, Month 0 to 18, and Month 0 to 24).
- Proportion of subjects free of new/newly enlarging T2 lesions up to Month 24 (Month 0 to EOS) and by visit (i.e., Month 0 to 6, Month 0 to 12, Month 0 to 18, and Month 0 to 24).

- [REDACTED]

Gd-enhancing lesions:

- Number of Gd-enhancing lesions per scan up to Month 24 (Month 0 to EOS) and number of Gd-enhancing lesions by visit (i.e., Month 6, Month 12, Month 18, and Month 24).
- Proportion of subjects free of Gd-enhancing lesions at EOS and by visit (i.e., Month 6, Month 12, Month 18, and Month 24).
- Volume of Gd-enhancing lesions at EOS and by visit (i.e., Month 6, Month 12, Month 18, and Month 24).

All MRI endpoints specified above will be summarized using descriptive statistics by treatment group and visit.

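### The primary relapse model could gain a little precision cheaply by adjusting for baseline Gd-enhancing lesions, which are already measured at screening

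*SAP*

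**What the plan says.** Protocol 9.4.2 tests the primary hypothesis "using treatment, number of relapses in the previous two years prior to screening, pubertal status, and region as covariates". SAP 4.2.1 has the same terms: "using treatment, pubertal status (the stratification factor in IVRS), and region as factors and number of relapses within the previous two year before randomization". No row of SAP Table 4-1 adds an MRI term, and neither does the Cox model for time to first relapse (SAP 4.2.2.3.1).

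Protocol 4.1 has two entry routes based on disease activity. One is clinical: "At least one MS relapse/attack during the previous year or two MS relapses in the previous two years prior to screening". The other is MRI alone: "or evidence of one or more Gd enhancing lesions on MRI within 6 months prior to randomization". The Amendment 4 rationale, which introduced the MRI route, describes clinical relapses and inflammatory MRI lesions as "both of which have been shown to be predictive of future MS relapse activity".

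The measurement is available. SAP 4.2.2.4 states: "Parameters collected at screening include: number and volume of T2 lesions, volume of T1 hypointense lesions, number and volume of Gd-enhancing lesions". SAP Table 4-2 adjusts the number of Gd-enhancing lesions per scan for the baseline Gd count, and the key secondary endpoint for baseline T2 lesions.

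**The concern.** The plan adjusts for a baseline MRI value where the outcome is MRI. It does not do so for the relapse endpoint, although the sponsor's own reasoning links MRI activity to relapse.

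The entry criteria sharpen this. A patient who enters on MRI alone fails the clinical route. Counting back from screening, that patient has no relapse in two years, or one that is more than a year old. Such patients sit at or near the bottom of the model's only disease-activity covariate although they were enrolled for active disease.

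Two things are at stake. Between-patient variation that a Gd term could explain stays in the dispersion parameter, so the interval for the ARR ratio is slightly wider than it need be. And with about 95 patients per arm, a chance imbalance in MRI activity is not adjusted for.

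**Working it through.** **Inputs from the documents** (protocol 9.6 and Appendix 5, SAP 9.1): ARR 0.18 versus 0.36, 95 per arm, T = 2 years, dispersion k = 0.82, two-sided alpha 0.05, information target 16.36. Expected relapses per patient are 0.36 and 0.72.

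**Assumed, because the documents do not give them:** Gd prevalence, the Gd-relapse rate ratio and the share of patients entering on MRI alone.

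**1. The plan's own figure.** Appendix 5, Equation 2:

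I = 95 / (1/0.36 + 1/0.72 + 2 × 0.82) = 95 / 5.807 = 16.36

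Power = Φ(ln 2 × √16.36 − 1.96) = Φ(0.844) = 80.1%. The stated design reproduces, and it contains no covariates.

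**2. Same formula with a Gd term.** For a binary Gd status with prevalence p and rate ratio r, the squared coefficient of variation it explains is CV² = p(1 − p)(r − 1)² / (1 − p + pr)². The remaining dispersion is k′ = 1.82/(1 + CV²) − 1.

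Example, p = 0.5 and r = 2: CV² = 0.25/2.25 = 0.111; k′ = 0.638; I = 95/(4.167 + 1.276) = 17.45; power 82.5%.

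| p | r | k′ | I | Power |
|---|---|---|---|---|
| 0.3 | 1.25 | 0.800 | 16.48 | 80.3% |
| 0.5 | 1.25 | 0.798 | 16.49 | 80.4% |
| 0.3 | 1.5 | 0.751 | 16.76 | 81.0% |
| 0.5 | 1.5 | 0.750 | 16.76 | 81.0% |
| 0.3 | 2.0 | 0.619 | 17.58 | 82.8% |
| 0.5 | 2.0 | 0.638 | 17.45 | 82.5% |
| 0.3 | 2.5 | 0.486 | 18.49 | 84.6% |
| 0.5 | 2.5 | 0.538 | 18.12 | 83.9% |

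These are upper figures, because Equation 2 gives every patient in an arm the same expected count. Once Gd is in the model, expected counts differ, and each patient contributes μ/(1 + k′μ). For p = 0.5 and r = 2, μ is 0.24 or 0.48 on fingolimod and 0.48 or 0.96 on interferon. The mean contributions are 0.2878 and 0.4814, so I = 95/(1/0.2878 + 1/0.4814) = 17.11 and power is 81.8%. The same step gives 82.0% at p = 0.3, r = 2, and 80.7% at r = 1.5 for either prevalence.

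**3. Simulation.** 190 patients were allocated 1:1 with two years each and total dispersion 0.82. The rate ratio was 1.2 per prior relapse; 10% or 20% entered on MRI alone (all Gd-positive, 0 or 1 prior relapse), and 45% of the rest were Gd-positive. Models contained treatment and prior relapses, with or without Gd; region and pubertal status were left out. Each setting had 593 to 600 fitted runs.

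- Mean standard error of the log rate ratio, true ratio 0.50: 0.2466 to 0.2451 at r = 1.5 (0.6% lower); 0.2457 to 0.2411 or 0.2413 at r = 2 (1.8-1.9% lower). With no treatment effect the falls were 0.8% and 2.4%.
- Bias without Gd at r = 1.5 and 2: mean rate ratio 0.498 to 0.503 against a true 0.50.
- Type I error: 4.5-4.7% without Gd, 5.0-5.5% with it (Monte Carlo error about 0.9 points).
- Observed over predicted relapses in MRI-only patients, model without Gd: 1.14-1.15 at r = 1.5, 1.18-1.25 at r = 2, and 0.98 when Gd has no effect.

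Monte Carlo error on simulated power is about 1.6 points, so the standard errors are the steadier comparison.

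**4. Chance imbalance.** With half the patients Gd-positive, the standard deviation of the between-arm difference in proportion is √(2 × 0.25/95) = 0.073, and 1.96 times that is 0.142. At r = 2 such a difference multiplies the crude rate ratio by (1.5 + 0.071)/(1.5 − 0.071) = 1.10 or its inverse. A ratio of 0.50 would then appear as about 0.55 or 0.455. This is random error, already covered by the confidence interval, but adjustment would remove part of it.

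**The case against.** The strongest reply is that nothing is wrong as written. Protocol and SAP agree on a pre-specified model with a sensible prognostic covariate, and the choice among such covariates belongs to the sponsor. That stands, and it rules out three stronger readings.

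- *The treatment effect is biased or the test invalid.* Randomization protects both. With a log-link rate model, an omitted balanced covariate moves into the dispersion, and the simulation shows neither bias nor type I inflation.
- *The trial falls short of 80% power.* The 80% was computed without covariates, and the Core Phase stops on blinded information from a pooled fit (protocol 9.6, SAP 9.1). Any gain comes on top of that target. The Amendment 7 rationale projected 96% power had the two-year duration been kept.
- *MRI-only patients are modeled as low risk.* This depends on a prior-relapse coefficient that the data will estimate. A patient with one older relapse has the same covariate value as one who entered on a single recent relapse.

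Other limits also stand. The predictive statement sits in an amendment rationale and concerns inflammatory MRI lesions generally, though the criterion it justified is current. Protocol 1.1 reports that lesions in children are less prone to enhance, which could shrink the gain. It cannot be said that baseline Gd is used only for Gd endpoints, because rows of SAP Table 4-4 are redacted. SAP 3.5.1 already summarizes baseline Gd by arm, so an imbalance would be visible, though not adjusted for. A qualifying scan may be up to six months old, so a patient who entered on Gd can have a clear screening scan and be coded 0.

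These points narrow the benefit. They do not remove the case for using a prognostic value already in hand.

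**Conclusion.** A worthwhile low-cost improvement, not a defect. The omission is plain in protocol 9.4.2, SAP 4.2.1 and Table 4-1, and the documents give no reason for it.

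For assumed Gd rate ratios of 1.5 to 2.0 and prevalence of 30-50%, planning power rises from 80.1% to about 81-83% by the protocol's formula, or about 80.7-82.0% once the spread of predicted rates is allowed for. The simulated standard error falls by about 0.6-1.9%. At a Gd rate ratio of 1.25 the gain is negligible. All these sizes rest on assumed Gd effects; only the direction follows from the documents, and only if Gd lesions do predict relapse in this population.

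**What to change.** Before unblinding:

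- Add baseline Gd-enhancing lesions (0 versus 1 or more on the last pre-dose MRI) to the negative binomial model in protocol 9.4.2, SAP 4.2.1, Table 4-1 and the code in SAP 10.1.1.1, and to the Cox model for time to first relapse.
- Keep every FAS patient in the analysis through a pre-specified, treatment-blind rule for missing baseline Gd, for example the most frequent category in the pooled data.
- Retain the present model as a supportive analysis in Table 4-1.
- Report the number of patients enrolled on MRI activity alone, by arm.

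Timing matters. SAP section 2 allows covariates to be dropped on non-convergence but not added, so a Gd term introduced after unblinding would look data-driven. If the sponsor will not change the primary model, protocol 9.4.4 leaves room to pre-specify the Gd-adjusted model as supportive.

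Cost: a protocol amendment under section 11.1 as well as an SAP amendment, one extra parameter, a missing-value rule, and some misclassification of patients whose qualifying scan preceded a clear screening scan.
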